4. INVESTIGATIONAL PLAN

4.1. Overall Study Design and Plan

DMID 14-0112 is a Phase II randomized, double-blind, placebo-controlled trial in a sample of 120 males and non-pregnant females, 18 to 49 years old, inclusive, who are in good health and meet all eligibility criteria. This clinical trial is designed to assess the safety, reactogenicity, and immunogenicity of two priming doses of M-001 followed by administration of IIV4.

Subjects are assigned randomly to 1 of 2 study arms (60 subjects per study arm) to receive two doses of the M-001 vaccine or placebo followed by a single dose of IIV4 (see Table 1).

- Group A receives two 1 mg doses of M-001, on Days 1 and 22 followed by a single dose of IIV4 on approximately Day 172 (±30).
- Group B receives saline placebo on both Days 1 and 22, followed by a single dose of IIV4 approximately on Day 172 (±30).

4.2. Discussion of Study Design, Including the Choice of Control Groups

This study uses a placebo concurrent control design. Saline was chosen to act as an inactive placebo control as a comparator for the safety, reactogenicity, and immunogenicity of two doses of M-001 vaccine as well as for the downstream immunogenic effects post-seasonal IIV4 vaccination.

4.3. Selection of Study Population

The study population for this clinical trial is 120 males and non-pregnant females, 18-49 years of age, inclusive, who meet all eligibility criteria. Eligibility criteria ensure that subjects are in good health at the time of vaccination and have not received (and do not plan to receive) therapies that would interfere with immune response to the study products, such as non-study vaccines or immunosuppressive therapies. Exact eligibility criteria can be found in the protocol sections 5.1 and 5.2. Subjects are recruited from the general population at the participating Vaccine Trial and Evaluation Unit (VTEU) sites that have substantial experience conducting large influenza vaccine studies.

4.4. Treatments

4.4.1. Treatments Administered

Two doses of either multimeric M-001 vaccine or saline placebo are administered per subject's randomized assignment, followed by administration of seasonal IIV4 vaccine to all subjects.

4.4.2. Identity of Investigational Product(s)

Seasonal Quadrivalent Inactivated Influenza Vaccine (IIV4)

IIV4 for intramuscular injection is indicated for active immunization against influenza disease caused by influenza virus subtypes A and type B present in the vaccine. The 2018-2019 Fluzone Quadrivalent IIV4 used in the study was formulated by Sanofi to contain HA of each of the following four influenza strains recommended for the 2018-2019 Northern Hemisphere influenza season: A/Michigan/45/2015 X-275 (H1N1), A/Singapore/INFIMH-16-0019/2016 IVR-186 (H3N2), B/Maryland/15/2016 BX-69A (a B/Colorado/06/2017-like virus, B Victoria lineage), and B/Phuket/3073/2013 (Yamagata lineage).

M-001

Multimeric-001 (M-001) vaccine developed by BiondVax is

Placebo

Sterile normal saline will be used as the placebo.

4.4.3. Method of Assigning Subjects to Study Arms (Randomization)

Enrollment/randomization is done through the enrollment module in the electronic data capture system, maintained by the SDCC.

Eligible subjects are randomized and assigned in a [1:1] ratio to receive two priming doses 21 days apart of either M-001 (Group A) or saline placebo (Group B), followed by seasonal IIV4 vaccination (all groups). Randomization is stratified by prior receipt of the 2017-2018 influenza vaccine and by site. The randomization is based on a variable blocked scheme to provide an approximately balanced allocation to the study arms during the study.

4.4.4. Selection of Doses in the Study

Multiple studies of M-001 have assessed the safety and immunogenicity profile in healthy adults, and their results suggested that immune responses were improved with increasing doses up to 1 mg, with no safety concerns identified. The 1 mg dosage was selected for this trial based on the elevated HAI antibody responses in that study group in the placebo-controlled BVX-006 trial [NCT02293317], where no SAEs or safety concerns were observed.

4.4.5. Selection and Timing of Dose for Each Subject

All subjects receive the assigned vaccination at Day 1 and Day 22 (+2 days), followed by a single dose of IIV4 on approximately Day 172 (±30 days).

4.4.6. Blinding

This trial is double-blinded; subjects, investigators, study personnel performing any study-related assessments following study vaccine administration, and laboratory personnel performing antibody assays are blinded to the treatment assignment.

The randomization scheme was generated by the SDCC and provided to unblinded study personnel (i.e., pharmacists performing study vaccination preparations and unblinded study vaccine administrators) at the participating VTEU sites who are not involved in study-related assessments or have subject contact for data collection following study vaccine administration.

The Data and Safety Monitoring Board (DSMB) receives data in aggregate and presented by group and may request treatment assignment be unblinded for an individual subject if required for safety assessment. The DSMB reviews grouped and unblinded data in the closed session only.

4.4.7. Prior and Concomitant Therapy

Concomitant medications include any medications, therapies, or vaccinations taken in the 60 days prior to Day 1 through approximately 21 days after the last M-001/placebo dose received. Medications reported in the electronic case report form (eCRF) are limited to those taken within 30 days prior to the first study

vaccination through approximately 21 days after the second M-001/placebo dose. In addition, receipt of any non-study vaccines is solicited at each clinic visit or phone call and reported in the eCRF for the entire duration of the study.

Use of new medication should prompt evaluation for the presence of a new diagnosis of chronic medical disease or condition. Medications that might interfere with the evaluation of the investigational product were not to be used unless absolutely necessary. Medications in this category include the prohibited medications per the Subject Exclusion Criteria. In addition, the site PI or appropriate staff may identify other mediations that should not be used due to a risk to subject safety or assessment of reactogenicity and immunogenicity.

4.4.8. Treatment Compliance

All subjects receive two doses of either M-001 or saline placebo followed by seasonal IIV4 administered in the clinic.

4.5. Immunogenicity and Safety Variables

See Table 2 for the schedule of study procedures in DMID protocol 14-0112.

4.5.1. Safety Variables

Safety will be assessed by the frequency and severity of:

- 1. All SAEs occurring from the time of the first study vaccination through the end of the study
- 2. Solicited AEs reactogenicity events occurring on the day of each study vaccination through 7 days after each M-001 study vaccination:
 - a) Injection site reactions including pruritus, ecchymosis, erythema, induration/swelling, pain, and tenderness.
 - b) Systemic reactions including fever, feverishness, fatigue, malaise, myalgia, arthralgia, headache, and nausea.
- 3. Unsolicited AEs non-serious AEs occurring from the time of the first M-001 study vaccination through approximately 21 days after the second M-001 study vaccination.
- 4. Safety laboratory abnormalities occurring from the time of the first study vaccination through 8 days after the last dose of M-001.
 - a) Clinical safety laboratory parameters measured: WBC, hemoglobin, platelets, ALT, total bilirubin, and creatinine

4.5.2. Immunogenicity Variables

Cellular immunogenicity data will be reported by the Baylor College of Medicine. These data will include the frequency of influenza-specific T cells as measured by fluorescence-based flow cytometric assays. The lab at Baylor will also report the percentage of influenza-specific T cells expressing discrete memory markers (CCR7, CD45RO, and CD57), the percentage of CD4 and CD8 T cells expressing perforin, CD107a, IFN- γ , TNF- α , and IL2, alone or in combination, the percentage of CD4+ T cell subsets expressing IL-4 or IL-17, T follicular helper (TFH) cells (CD4+, CXCR5+, PD-1+, IL-21+) , T follicular regulatory (Tfr) cells (CXCR5+, PD-1+, CD25+, CD127+) , and T regulatory cells (Tregs) (CD25+, Foxp3+)as measured by flow cytometry.

Individual HAI and Neut antibody results will be reported for the IIV4 vaccine strain by the central immunology laboratory at St Louis University. Assay results are reported as a reciprocal titer with values of $10*2^k$, where k=0, 1, 2, etc. The lower limit of detection for both the HAI and Neut assays is 1:10; values below the limit of detection are reported as '<10', and for analysis are imputed as one-half the limit of detection (10/2 = 5). For analysis, the geometric mean of repeated results for each sample will be computed and used as the response for all subsequent calculations. The variation arising from multiple measurements for an individual at a single time point will not be used in subsequent calculations. See Section 3.3 for definitions of derived variables for the analysis of HAI and Neut data.

Assays to determine serum levels of antibodies to M-001 will be performed by BiondVax.

5. SAMPLE SIZE CONSIDERATIONS

The study population for this clinical trial was planned to include 120 males and non-pregnant females, 18 to 49 years old, inclusive, who are in good health and meet all eligibility criteria. The subjects were recruited from the general population at the participating VTEU sites that have substantial experience conducting large influenza vaccine studies.

Based on the accrual rate for similar studies, it was expected that the participating VTEUs would be able to enroll this trial in a timely fashion. Prior experience suggests up to 5% of subjects could be excluded from the per protocol analysis for the primary immunogenicity outcome either because they are lost-to-follow-up or otherwise do not have data available following the second study vaccination or because they had a protocol deviation requiring their exclusion from the per protocol analysis.

Table 3 indicates the probability of observing one or more safety events, such as solicited injection site or systemic reactogenicity events or an unsolicited non-serious AE of a particular type, for a single study arm (N=60) and all enrolled subjects (N=120).

Binomial confidence intervals (CI) are widest (have the least precision) when the response rate is 50%. Table 4 is presented to indicate the worst-case scenario for precision of observed exact (Clopper-Pearson) binomial confidence intervals.

With N=60 subjects per arm and assuming the standard deviation of log GMP is 0.75, the study will have 80% power to detect a 2.5-fold increase in the GMP of T cell subsets expressing IFN-γ. Table 5 illustrates a power analysis considering a range of standard deviations for log GMP and a range of GMP fold-change with N=60 subjects per arm, and further includes the power under the conservative assumption of 10% drop out in each study arm. Power is calculated for a two-sided t-test with significance level (alpha) 0.05 using PROC POWER in SAS 9.4. Utilizing different tests instead of those based on Normal approximations could increase the power from what is shown.

While there will be multiple comparisons performed for this primary immunogenicity objective (for each of five parameters alone measured in CD4 and CD8 T cells plus any combinations measured), it is assumed that these analyses are not intended to be confirmatory and thus no adjustment for multiple comparisons is considered. Instead, p-value thresholds of p<0.001, p<0.01, and p<0.05 will be considered as strong, moderate, and weak evidence of differences between study arms. These will be indicated in relevant tables with ***, **, and *, respectively.

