12. SUMMARY OF CHANGES IN THE CONDUCT OF THE STUDY OR PLANNED ANALYSES

After the data format for the primary analysis was confirmed, the planned analysis was changed from what is described in the protocol. Instead of utilizing a normal approximation, a Poisson regression model will be fit to test for differences between study arms, as described in Section 8.1.

Additionally, the modified Intent-to-Treat population will only be used as a sensitivity analysis for the primary objective. Originally it was also planned for secondary and exploratory objectives involving antibody responses, but these will not be done in the interest of conciseness.

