9.7.1 Sample Size

Table 3: Power (%) to Detect Safety Events

Event Frequency	Single Study Arm N=60	Two Study Arms N=120
≥10% Very Common	99.8	>99.9
≥1% Common	45.3	70.1
≥0.1% Uncommon	5.8	11.3
≥0.01% Rare	<1	1.2

Table 4: Precision of Binomial Confidence Intervals

	N	95% CI
Single Study Arm	60	(36.8, 63.2)
Two Study Arms	120	(40.7, 59.3)

Table 5: Power Analysis for Primary Immunogenicity Endpoint

GMP _e /GMT _c {fold-change}	$\begin{array}{c} log_{10}\left(GMP_{M}\right) - log_{10}\left(GMP_{c}\right) \\ \{log\text{-}difference}\} \end{array}$	Std Dev log ₁₀ (GMP)	Power (N = 60)	Power (N=54) 10% drop out
		0.25	97	96
1.5	0.18	0.50	49	45
		0.75	26	23
		0.25	>99	>99
2	0.30	0.50	90	87
		0.75	58	54
		0.25	>99	>99
3	0.48	0.50	>99	99
		0.75	93	90
		0.25	>99	>99
4	0.60	0.50	>99	>99
		0.75	99	98

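### The SAP's 80% power belongs to a log-scale t-test that the SAP has replaced; no power is given for the Poisson count model, and the remark that other tests could raise power is unsupported for it

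*SAP*

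**What the plan says.** SAP Section 5 repeats the protocol's planning statement (Protocol 11.3.4): "assuming the standard deviation of log GMP is 0.75, the study will have 80% power to detect a 2.5-fold increase in the GMP". It names the test behind the figure: "Power is calculated for a two-sided t-test with significance level (alpha) 0.05 using PROC POWER in SAS 9.4". Table 5, titled "Power Analysis for Primary Immunogenicity Endpoint", extends this to SDs of 0.25, 0.50 and 0.75 on the log10 scale, with 60 and 54 per arm. The SAP then adds a sentence that the protocol does not have: "Utilizing different tests instead of those based on Normal approximations could increase the power from what is shown".

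Protocol 11.5.4 planned the matching t-test. SAP Section 12 withdraws it: "Instead of utilizing a normal approximation, a Poisson regression model will be fit to test for differences between study arms". Section 8.1 defines the replacement as a log-linear Poisson model for the count of positive cells, with one indicator for arm, total T cells as the offset, and Wald tests. Neither Section 8.1 nor the Table 22 footnote mentions a dispersion parameter or robust standard errors. No power is given for this model anywhere.

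**The concern.** A power figure is a property of a particular test. The t-test compares geometric means on the log scale. With one arm indicator and an offset, the Poisson model's rate ratio is pooled positive cells over pooled total cells in one arm, divided by the same quantity in the other. That compares cell-weighted arithmetic means. When responses are strongly right-skewed, a few high responders dominate an arithmetic mean, and a comparison on that scale can be much less precise.

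The stake is how the primary T-cell result is read. A reader would take it as coming from a design with 80% power at 2.5-fold, and would take the added sentence as a sign that the change of test could only have helped. Neither follows for the analysis now planned.

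**Working it through.** **Inputs from the documents.** 60 per arm, 1:1; SD 0.75 on log10; 2.5-fold, so a log10 difference of 0.398; two-sided alpha 0.05 (SAP 4.4.3, 5, Table 5). Up to 5% per-protocol exclusions gives 57 per arm; 10% dropout gives 54.

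**1. The plan's own figure.** Noncentrality = 0.398 / (0.75 × √(2/n)). At n = 60 this is 0.398 / 0.1369 = 2.91.

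| n per arm | t-test power |
|---|---|
| 60 | 82.2% |
| 57 | 80.2% |
| 54 | 78.0% |

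The stated 80% is reproduced to rounding; at n = 60 it corresponds to 2.44-fold. Table 5 is reproduced within about 2 points.

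**2. What changes with the scale.** A t-test planned on log10 percentages implies log-normal percentages. With σ = 0.75 × ln 10 = 1.727, the between-subject CV is √(exp(σ²) − 1) = √18.73 = 4.33. It is 1.66 at SD 0.50 and 0.63 at SD 0.25. With equal SDs the ratio of arithmetic means is still 2.5, so the target effect is unchanged and only precision is lost. The large-sample standard error of the log ratio is √(2 × 18.73 / 60) = 0.79 for arithmetic means, against 1.727 × √(2/60) = 0.315 on the log scale. At this skewness the large-sample formula is crude (it implies about 21% power), so power was simulated.

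**3. Simulation.** Log-normal subject rates, Poisson counts given the rate, 60 per arm. Assumptions not in the documents: 20,000 to 100,000 T cells per sample, equal across subjects, and a control geometric mean of 0.01% to 0.1%. The t-test on the same simulated data used log10((count + 0.5)/cells). Results at SD 0.75:

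| Test | Rejects, no difference | Rejects, 2.5-fold |
|---|---|---|
| Plain Poisson Wald (as written) | 81-98% | 96-99% |
| Quasi-Poisson | about 5% | 42-45% |
| Permutation of the log ratio of means | about 5.5% | about 49% |
| Welch test on raw percentages | about 3% | about 37% |
| Sandwich standard errors | about 11% | about 57% |
| t-test on log10 | about 5% | 76-82% |

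The plain Wald test's null rejection exceeds 90% in all but the sparsest settings (0.01% with 20,000 or 50,000 cells: 81% and 88%). The sandwich version does not hold its size, so its 57% is left out of the valid range. At 54 per arm, quasi-Poisson power is about 41%.

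**4. Dependence on SD and fold-change (60 per arm).**

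| Fold, SD | Quasi-Poisson | t-test on log10 |
|---|---|---|
| 2.5, 0.75 | 42-45% | 82% |
| 3, 0.75 | 55-56% | 93% |
| 2, 0.50 | about 70% | 90% |
| 2.5, 0.50 | about 89% | 99% |
| 2.5, 0.25 | about 100% | about 100% |

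**The case against.** Several points on the other side are fair.

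- **No figure is miscalculated.** A reader might infer an arithmetic error. There is none: the 80% and Table 5 are right for the test they name, the SAP names it, and Section 12 discloses the change. This stands. The fault is that the figure was carried over, under a title referring to the primary endpoint, to an analysis it does not describe.
- **The corrected-variance power is not that of the planned test.** A reader might infer that the trial, as planned, would miss a 2.5-fold effect more often than find it. The documents do not support that. The test in Section 8.1 would reject nearly always, with or without an effect, so its first problem is type I error. The 37-49% applies only once the variance is corrected and the pooled-rate scale kept.
- **The sentence is hedged and general.** It says could and names no test. But Section 12 describes the new model as the replacement for a normal approximation, so readers will connect the two, and nothing in the SAP supports a gain for this model.
- **The log-scale test has its own difficulty.** The primary tables include many marker combinations, and the Listing 18 note anticipates zero percentages, which have no logarithm. The SAP gives no rule for them. In sparser simulations (50,000 cells, median 0.0005-0.001%) the t-test itself fell to 60-67%. This stands and shapes the fix.
- **The analyses are declared non-confirmatory.** That limits the consequences, since no decision rule depends on the 80%. It does not make the figure apply, and Section 5 still grades p-values as evidence.

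**Conclusion.** The point holds in this form. The stated power belongs to a comparison the SAP no longer runs, none is given for its replacement, and the sentence suggesting a gain is unsupported for that replacement.

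At the planning values (2.5-fold, SD 0.75, 60 per arm), methods on the pooled-rate scale that held their size gave about 37-49%, with quasi-Poisson at about 44%, against 82% for the t-test in theory. The direction was the same across the assumed cell counts and baselines. The size of the loss rests on log-normal percentages, an SD near 0.75 and the choice of variance correction. At SD 0.50 the gap is about 10 points at 2.5-fold, and at SD 0.25 it is negligible for that effect. The 44% is therefore one conditional value, neither a figure from the documents nor the power of the Wald test as written.

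**What to change.** 1. Delete the Section 5 sentence quoted above about different tests.
2. State in Section 5 and in the Table 5 title that the 80% and the table apply only to the two-sided t-test on log10 percentages.
3. Then choose one of two routes:
   - run that log-scale comparison as the analysis the power claim supports, with a prespecified rule for zero counts; or
   - if the count model stays primary, replace the 80% and the Table 5 entries with simulated power for an overdispersion-corrected version, listing the assumed distribution, SD, cell totals and baseline frequencies, and giving the range rather than a single value.

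The cost is SAP wording and one short simulation, with no extra subjects or samples. On the second route the stated power becomes less favourable at the larger SDs; on the first, a zero-count rule has to be defined and defended for the sparse marker combinations.

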11. STATISTICAL CONSIDERATIONS

11.1. Study Hypotheses

The study is not designed to test a specific hypothesis for the primary safety objectives. Nevertheless, this trial represents an important opportunity to extend the M-001 safety base.

The primary immunogenicity objective is to determine whether priming with M-001 improves T cell responses. The hypothesis that will be tested is:

$$H_0: GMP_M/GMP_c = 1 \rightarrow \log_{10}(GMP_M) - \log(GMP_c) = 0$$

$$H_1: GMP_M/GMP_c \neq 1 \rightarrow \log_{10}(GMP_M) - \log(GMP_c) \neq 0$$

Where GMP_M and GMP_c are the geometric mean percentage (GMP) percentage of T cell subsets expressing perforin, CD107a, INF γ , TNF- α , and IL-2 for the M-001 and control (placebo) treatment arms, respectively.

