11.3.4. Sample Size

This study is planned to enroll 120 subjects (60 per treatment arm). The following illustrates the precision and power that is available for select estimates and comparisons of interest.

[Table 8](#) indicates the probability of observing one or more safety events, such as solicited injection site or systemic reactogenicity events or an unsolicited non-serious AE of a particular type, for a single treatment arm (N=60) and all enrolled subjects (N=120).

Table 8: Power (%) to Detect Safety Events

Event Frequency	Single Treatment Arm N=60	Two Treatment Arms N=120
≥10% Very Common	99.8	>99.9
≥1% Common	45.3	70.1
≥0.1% Uncommon	5.8	11.3
≥0.01% Rare	<1	1.2

Binomial confidence intervals (CI) are widest (have the least precision) when the response rate is 50%. [Table 9](#) is presented to indicate the worst case scenario for precision of observed exact (Clopper-Pearson) binomial confidence intervals.

Table 9: Precision of Binomial Confidence Intervals:

	N	95% CI
Single Treatment Arm	60	(36.8,63.2)
Two Treatment Arms	120	(40.7, 59.3)

With N = 60 subjects per arm and assuming the standard deviation of logGMP is 0.75, the study will have 80% power to detect a 2.5-fold increase in the GMP of T cell subsets expressing IFN- γ . [Table 10](#) illustrates a power analysis considering a range of standard deviations for log GMP and a range of GMP fold-change with N=60 subjects per arm, and further includes the power under the conservative assumption of 10% drop out in each treatment arm. Power is calculated for a two-sided t-test with significance level (alpha) 0.05 using PROC POWER in SAS 9.4.

While there will be multiple comparisons performed for this primary immunogenicity objective (for each of five parameters alone measured in CD4 and CD8 T cells plus any combinations measured), it is assumed that these analyses are not intended to be confirmatory and thus no adjustment for multiple comparisons is considered.

Table 10: Power Analysis for Primary Immunogenicity Endpoint

GMP _e /GMT _c {fold- change}	$\log_{10}(\text{GMP}_M) - \log_{10}(\text{GMP}_c)$ {log-difference}	Std Dev \log_{10} (GMP)	Power (N = 60)	Power (N=54) 10% drop out
1.5	0.18	0.25	97	96
		0.50	49	45
		0.75	26	23
2	0.30	0.25	>99	>99
		0.50	90	87
		0.75	58	54
3	0.48	0.25	>99	>99
		0.50	>99	99
		0.75	93	90
4	0.60	0.25	>99	>99
		0.50	>99	>99
		0.75	99	98

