6.8. Multiple Comparisons/Multiplicity

While there will be multiple comparisons performed for the primary immunogenicity objective (for each of five parameters alone measured in CD4 and CD8 T cells plus any combinations measures), it is assumed that these analyses are not intended to be confirmatory and thus no adjustment for multiple comparisons is considered

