8.1. Primary Immunogenicity Analysis

The primary immunogenicity objective is to determine whether priming with M-001 improves T cell responses. The cells are sorted via flow cytometry, and the percentages of CD4+ and CD8+ T cells expressing perforin, CD107a, IFN γ , TNF- α , IL-2, or any combination of these are calculated as the number of cells positive for these proteins divided by the total number of T cells counted in each sample. To compare the T cell responses between groups, the following Poisson regression model will be fit for each combination of proteins of interest:

$$log(E(Y|X)/Z)=\beta_0+\beta_1*X,$$

where Y is the number of cells expressing a given combination of proteins, X is an indicator variable for Group A, and Z (the offset) is the total number of T cells in each sample. Wald tests will be performed to evaluate whether there are differences in the expression of T cell subsets between the two study arms. As described in Section 6.8, adjustments for multiple comparisons are not planned.

GMPs of CD4+ and CD8+ T cells expressing each combination of proteins and the corresponding 95% bootstrap confidence intervals will also be presented for each study armTable 22Table 23Table 24Table 25. These will be presented in Table 22, Table 23, Table 24, and Table 25 and summarized visually in boxplots over time in Figure 2, Figure 3, Figure 4, and Figure 5.

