[Implementation Note: Do not include p-value column for Tables 28-31, and only include it for Day 36 for Tables 25-27. Include rows for any perforin, any CD107a, any IFN- γ , any TNF- α , and any IL2.]

- Table 23: Geometric Mean Percentage (GMP) of CD8+ T Cell Subsets Expressing Markers Alone or in Combination After M-001 Stimulation with 95% Confidence Intervals by Study Day and Study Arm, Per Protocol Population*
- Table 24: Geometric Mean Percentage (GMP) of CD4+ T Cell Subsets Expressing Markers Alone or in Combination After M-001 Stimulation with 95% Confidence Intervals by Study Day and Study Arm, Modified Intent-to-Treat Population*
- Table 25: Geometric Mean Percentage (GMP) Of CD8+ T Cell Subsets Expressing Markers Alone or in Combination After M-001 Stimulation with 95% Confidence Intervals by Study Day and Study Arm, Modified Intent-to-Treat Population*
- Table 26: Percentage of CD4+ T Cell Subsets Expressing Markers Alone or in Combination After Seasonal Influenza A Antigen Stimulation with 95% Confidence Intervals by Study Day and Study Arm, Per Protocol Population
- Table 27: Percentage of CD8+ T Cell Subsets Expressing Markers Alone or in Combination After Seasonal Influenza A Antigen Stimulation with 95% Confidence Intervals by Study Day and Study Arm, Per Protocol Population
- Table 28: Percentage of CD4+ T Cell Subsets Expressing Markers Alone or in Combination After Pandemic Influenza A Antigen Stimulation with 95% Confidence Intervals by Study Day and Study Arm, Per Protocol Population
- Table 29: Percentage of CD8+ T Cell Subsets Expressing Markers Alone or in Combination After Pandemic Influenza A Antigen Stimulation with 95% Confidence Intervals by Study Day and Study Arm, Per Protocol Population

^{*}Wald test from Poisson regression used to compare groups.

^{95%} CIs calculated via 10,000 bootstrap samples.

Table 30: Summaries of Hemagglutination Inhibition Antibody Against A/Michigan/45/2015 X-275 (H1N1) by Study Day and Study Arm, Per Protocol Population

	Group A: 1 mg M-001 (N=X)	Group B: Placebo (N=X)
Day 1		
n	x	X
GMT (95% CI)	xxx.x(xxx.x,xxx.x)	xxx.x(xxx.x,xxx.x)
Titer ≥ 1:40 - %(95% CI)	x.x (x.x, x.x)	x.x (x.x, x.x)
Day 22		
n	x	X
GMT (95% CI)	xxx.x(xxx.x,xxx.x)	xxx.x(xxx.x,xxx.x)
Seroconversion - %(95% CI)	x.x (x.x, x.x)	x.x (x.x, x.x)
Titer ≥ 1:40 - %(95% CI)	x.x (x.x, x.x)	x.x(x.x, x.x)
Day 43		
n	x	X
GMT (95% CI)	xxx.x(xxx.x,xxx.x)	xxx.x(xxx.x,xxx.x)
Seroconversion - %(95% CI)	x.x (x.x, x.x)	x.x(x.x, x.x)

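### One primary T-cell hypothesis is tested by 74 unadjusted p-values with no lead row, and each raw p-value is graded as evidence without regard to the number of tests

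*SAP*

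**What the plan says.** - **Hypothesis.** Protocol 11.1: "The primary immunogenicity objective is to determine whether priming with M-001 improves T cell responses". It continues "The hypothesis that will be tested is" and gives a single two-sided null, that the ratio of geometric mean percentages (GMP) is 1.
- **Power.** Protocol 11.3.4, repeated in SAP 5: "the study will have 80% power to detect a 2.5-fold increase in the GMP of T cell subsets" expressing IFN-γ, with a log SD of 0.75 and 60 per arm. No cell type is given, and no other marker has its own power statement.
- **Tests.** SAP 8.1: a "Poisson regression model will be fit for each combination of proteins of interest", with a Wald test for each. SAP 5 describes the comparisons as "for each of five parameters alone measured in CD4 and CD8 T cells plus any combinations measured".
- **Rows.** The Table 22 shell lists every positive/negative pattern of the five markers under its primary-endpoint heading for Day 36. It then lists one row per marker regardless of the others; the note below it reads "Include rows for any perforin, any CD107a, any IFN" and so on. Table 23 repeats this for CD8+ cells. Tables 24 and 25 repeat both in the modified intent-to-treat (mITT) set, which SAP 8 calls a sensitivity analysis.
- **Multiplicity.** SAP 6.8: the analyses are not meant to be confirmatory, so "no adjustment for multiple comparisons is considered". SAP 5 then offers graded thresholds in place of an adjustment: "p-value thresholds of p<0.001, p<0.01, and p<0.05 will be considered as strong, moderate, and weak evidence of differences between study arms", marked with one to three stars.

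**The concern.** A primary hypothesis in the singular, with a power claim at two-sided 0.05, implies one identifiable test that answers it. The plan has none. IFN-γ stands alone only in the sample size sentence, and nothing links that sentence to a row of Table 22 or 23.

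The grades add to this. A raw p-value below 0.01 means one thing for a single pre-named test and another for the smallest of 74. The SAP gives both the same label and never states how many labelled rows chance alone would produce.

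This matters because Tables 22 to 25 carry the asterisk that marks topline content, and Protocol 11.5 says the topline report may be published and used to plan later trials. A reader would see starred rows with no pre-specified answer to the primary question and no yardstick for the stars.

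**Working it through.** **1. The plan's own power figure.** Inputs (Protocol 11.3.4, SAP 5): 2.5-fold, SD 0.75 on the log10 scale, two-sided t-test at 0.05.
- Noncentrality = log10(2.5)/0.75 × √(n/2).
- n = 60: 0.398/0.75 × √30 = 2.906; critical t 1.980; power 82.2%.
- n = 57 (60 × 0.95, the plan's 5% exclusion from PP): 2.833; power 80.2%.

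The stated 80% is reproduced, most closely at 57 per arm. It is the power of one test at 0.05.

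**2. Row count.** Five markers give 2^5 = 32 patterns, including all-negative. Adding 5 any-marker rows gives 37. Two cell types give 37 × 2 = 74.

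One caveat concerns the note under Table 22. It says which similar tables carry p-values but cites Tables 25-27 (Day 36 only) and 28-31 (none), whereas the similar tables are now 23 to 29. Subtracting 2 gives 23-25 and 26-29, which fits the titles: M-001 stimulation with p-values, seasonal and pandemic antigens without. So 74 rests on evident intent.

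**3. Expected chance findings**, whatever the correlation, if there is no effect and each test holds its level:
- p<0.05: 74 × 0.05 = 3.7
- p<0.01: 74 × 0.01 = 0.74
- p<0.001: 74 × 0.001 = 0.074

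Without the two all-negative rows the first figure is 72 × 0.05 = 3.6, so the count is not sensitive to them.

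**4. Chance of at least one such row.** For independent rows this is 1 − (1 − α)^74 in either direction, and 1 − (1 − α/2)^74 favouring M-001. At 0.05 these are 1 − 0.95^74 = 97.8% and 1 − 0.975^74 = 84.6%.

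The rows are not independent: the 32 patterns partition the same cells and the any-marker rows are sums of them. The documents give no correlation, so I assume a common correlation ρ between 74 normal test statistics and integrate over the shared component.

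| | ρ = 0 | 0.3 | 0.5 | 0.7 |
|---|---|---|---|---|
| p<0.05, either direction | 97.8% | 89.4% | 71.1% | 45.7% |
| p<0.05, favouring M-001 | 84.6% | 52.1% | 36.4% | 22.9% |
| p<0.01, either direction | 52.5% | 38.1% | 25.5% | 14.8% |
| p<0.01, favouring M-001 | 31.0% | 19.2% | 12.8% | 7.4% |

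A simulation that built in the 32-pattern and 5-margin structure gave similar either-direction values (69% and 23% at ρ = 0.5, for 0.05 and 0.01).

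**5. Effect of adjustment.** In simulation of 74 rows with no effect, the chance of any Benjamini-Hochberg rejection at 5% was 5.1%, 4.5%, 3.4% and 2.4% at the same four correlations.

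**The case against.** The strongest defence is that the plan discloses all of this. Protocol 11.3.4 and SAP 5 and 6.8 state the multiple comparisons, call the analyses non-confirmatory and decline to adjust. The graded scale is offered as an alternative to a single 0.05 cut-off and calls p<0.05 only weak. In a phase II immunology panel that is a defensible choice. Nor did the SAP break up a single-marker endpoint: Protocol 3.2.1 already defines the outcome over five markers, alone or combined, in both cell types. This all stands, and it means strict family-wise control is not required.

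It does not cover two things. Non-confirmatory status excuses the lack of error control, but it does not make an evidence grade independent of the number of rows graded. Nor does it explain why a stated and powered hypothesis has no designated test.

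Two stronger readings are tempting, and the figures support neither:
- A reader might infer that graded evidence in favour of M-001 is likely by chance. At p<0.01 it is 31% even under independence and 7% to 19% at the assumed correlations. SAP 5 itself speaks of differences between arms, not of benefit.
- A reader might infer that starred rows are certain whether or not the vaccine works. At ρ = 0.7 the chance is 46%. Sparse marker combinations, which the note to Listing 18 anticipates by omitting zero percentages, would add less than a full test each.

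**Conclusion.** The point holds as a gap in the plan, not as a fatal flaw. One stated hypothesis has 74 primary PP p-values and no lead row, and the evidence grades take no account of that number. With no effect, 3.7 rows are expected below 0.05. At least one chance star in either direction is likely unless rows are strongly correlated (98% down to 46% over the assumed range).

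This rests on three assumptions: the count of 74 follows the evident intent of the outdated table note; the correlations are assumed; and each row's p-value is valid. If the Poisson Wald tests did not hold their level, the rates would differ. The power figures are for the protocol's t-test and do not describe the Poisson Wald test that replaced it (SAP 8.1 and 12).

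**What to change.** Before unblinding:
- **SAP 6.8 and 8.1:** name one lead row for the Protocol 11.1 hypothesis: any IFN-γ, Day 36, PP, in one stated cell type. IFN-γ is the only marker with a stated power; the team must choose CD4+ or CD8+, since the documents do not. Test it at two-sided 0.05 and call all other rows supportive.
- **Tables 22 and 23:** print Benjamini-Hochberg adjusted p-values beside the raw ones, with the family defined as the other 73 PP rows (74 − 1). Treat Tables 24 and 25 the same way, as a separate mITT sensitivity family.
- **Footnote:** state that 3.7, 0.74 and 0.07 of the 74 rows are expected below 0.05, 0.01 and 0.001 by chance.
- **Note under Table 22:** correct the table numbers so that it is clear which tables carry p-values.

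Raw p-values and the non-confirmatory status stay. Moving the stars to the adjusted values is optional: it makes the grades reflect the number of tests, at the price of fewer stars.

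The cost is some wording, one column, and fewer rows that look notable after adjustment. On the t-test basis, one lead row keeps 82% power at 60 per arm and 80% at 57. Two lead rows sharing 5% by Holm would have 74% at the first step (α = 0.025, 60 per arm). Bonferroni over all 74 rows (α = 0.05/74 = 0.00068) would leave 29%, and is not proposed.
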